The continuing working treatment hypothesis is that low-dose hydroxychloroquine is comparable to phlebotomy in time to remission. The study is conducted under an active IND (IND 66,042). It is likely that this study will define treatment guidelines and improved management of PCT. It also develops standards for time to specific outcomes for phlebotomy and low-dose hydroxychloroquine, which are not currently available and can be used for comparing future treatment approaches for PCT.

1.B Overview

Brief Summary

The purpose of this study is to determine whether a low dose regimen of hydroxychloroquine achieves remission as rapidly and safely as phlebotomy in the treatment of porphyria cutanea tarda (PCT).

Detailed Description

Porphyria cutanea tarda (PCT) is the most common and also the most readily treated form of porphyria. Repeated phlebotomy is the most widely used therapy in the U.S., but has disadvantages that include discomfort, inconvenience and expense. A low-dose regimen of the 4-aminoquinoline antimalarial drugs, either hydroxychloroquine or chloroquine, is also effective, and is more convenient and less expensive, but has not been widely adopted as first line therapy. Prospective data comparing these treatments are lacking, as are guidelines for selecting the most appropriate treatment for individual patients with PCT.

Study Hypothesis: Treatment of PCT by low-dose hydroxychloroquine, which has known advantages in terms of cost and convenience, can achieve remission as rapidly and safely as treatment by phlebotomy, and the durability of treatment is also comparable.

Comparison(s): This study compares treatment with a low-dose regimen of hydroxychloroquine to treatment by repeated phlebotomy. The primary outcome is time to achieving a normal plasma porphyrin concentration. Secondary outcomes include correction of additional porphyrin abnormalities that are expected with complete remission, and recurrence rates during long term follow up.

Significance: The results will guide clinical practice by providing a basis for selecting which of these standard treatments should be used in individuals with PCT. It will also provide data on time to treatment outcomes with both therapies that can be used for evaluating future therapeutic approaches. The pragmatic design of this study will lead to results that are more immediately applicable to clinical practice and relevant to cost-benefit considerations.

2. Background

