Liver ultrasound and biopsy will be recommended to participants based on clinical indications per the investigator, these tests will not be done solely for the study. If completed at an outside institution records will be obtained. Tissue will be examined microscopically, and iron content will be measured if possible. Evaluation of liver histology is not required for this study because the results are usually not essential for diagnosis or classification of PCT participants, identifying risk factors, or deciding on treatment options. However, liver biopsy is the best means of assessing liver iron concentration, and is often recommended for assessing the degree of pretreatment damage to the liver associated with hepatitis C, alcohol, steatosis, etc. Results of liver biopsy, when available, will be recorded on the CRFs and tabulated and analyzed with other clinical information that pertains to PCT.

Treatment assignment. Before assigning treatment, subjects will be evaluated for the contraindications to treatment with hydroxychloroquine and phlebotomy listed in Table 3 and 4.

If one of these treatments is contraindicated, the reason(s) will be recorded, and the subject will be assigned to the other treatment. Participants eligible for both will be assigned by randomization.

Table 3. Contraindications to treatment with hydroxychloroquine.

- 1. Unwillingness to consider this form of treatment
- 2. Lactating women
- 3. Psoriasis
- 4. Significant retinal disease
- 5. Glucose-6-phosphate dehydrogenase deficiency
- Recent and continued heavy use of alcohol (defined as 28 or more drinks per week)
- 7. Recent and continued use of hepatotoxic drugs such as acetaminophen, isoniazid or valproic acid
- Marked abnormalities in liver function tests at baseline, such as serum bilirubin >3mg/dL, serum alanine aminotransferase >200 U/L, or prothrombin time >16 seconds (or INR >1.4)
- 9. Advanced renal disease, with serum creatinine >3 mg/dL
- 10. Poor tolerance or poor response to this treatment in the past
- 11. HFE genotypes C282Y/C282Y or C282Y/H63D and serum ferritin above the normal range (>336 ng/mL)
- 12. Substantial iron overload, with serum ferritin >500 ng/mL, in the absence of these *HFE* genotypes
- 13. Marked iron overload (3+ or 4+) on liver biopsy, if available

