A total of at least 100 participants will be assigned, based on medical criteria, preference, or (if eligible for both treatments) by randomization, to one of these standard treatment groups. CRFs will be completed for each patient, including porphyrin levels, and data entered into the study database. This database is designed by and housed at the Data Management and Coordinating Center (DMCC) at the University of South Florida in Tampa. The DMCC is supported by the NIH Rare Diseases Clinical Research Network and serves as the secure repository for de-identified data for all consortia in the Network. Upon approval from the UTMB IRB and the Porphyrias Consortium DSMB, data from patients previously enrolled in this study at UTMB starting in 2006 before the study was a RDCRN study will be entered into the database. Subjects will be contacted to give their consent for this data transfer to the DMCC and storage in a federal data repository. For subjects who are now deceased consent will be obtained from next of kin. For subjects who cannot be re-contacted or where the next of kin cannot be re-contacted, approval of the UTMB IRB and the Porphyrias Consortium DSMB will be sought for this data transfer. Transferring this previously collected de-identified data is not expected to cause any increased risks to subjects. Data will be verified and edited where necessary for completeness and consistency by comparison with source documents. Study outcomes, such as time to achieving biochemical endpoints, will be determined from this data. As was found in the interim analysis, assignment to the two groups is unlikely to be equal, and more will be assigned to phlebotomy than to hydroxychloroquine. As in the interim analysis, times to achieving measures of remission are not expected to be substantially different for the two treatment groups. Effects of multiple susceptibility factors and other clinical and demographic features on treatment response and durability will be further examined. Outcome measures such as time to remission will be compared using Cox proportional models to study the effects of susceptibility factors on the hazard ratio to compare the two treatments. All patients who start treatment will be included in the analysis. Safety measures will be compared more descriptively where the adverse effects of each type of treatment are different.

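### The assignment rules place hepatic, heavy-alcohol and advanced-renal risk only in the phlebotomy group, so the pooled safety tables cannot support the safety half of the hypothesis

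*Combined protocol and SAP*

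**What the plan says.** 1.B Overview (Study Hypothesis) states that low-dose hydroxychloroquine "can achieve remission as rapidly and safely as treatment by phlebotomy, and the durability of treatment is also comparable". The Brief Summary in the same section gives the study's purpose in similar terms.

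4.E checks participants against Table 3 (contraindications to hydroxychloroquine) and Table 4 (contraindications to phlebotomy) before assignment. The rule is: "If one of these treatments is contraindicated, the reason(s) will be recorded, and the subject will be assigned to the other treatment". Those eligible for both are randomized. Four Table 3 items matter here:

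- item 6: continued drinking at 28 or more drinks a week;
- item 7: "Recent and continued use of hepatotoxic drugs such as acetaminophen, isoniazid or valproic acid";
- item 8: "Marked abnormalities in liver function tests at baseline, such as serum bilirubin >3mg/dL, serum alanine aminotransferase >200 U/L, or prothrombin time >16 seconds" (or an INR above 1.4);
- item 9: serum creatinine above 3 mg/dL.

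Table 4 has four items: unwillingness, severe marrow dysfunction with anemia, poor venous access, and poor past tolerance or response.

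4.R describes two groups with no substudy. It says "All patients who start treatment will be included in the analysis" and, in the next sentence, "Safety measures will be compared more descriptively where the adverse effects of each type of treatment are different".

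Other sections point away from a safety comparison. 4.B says that comparing safety is not an objective. 5.H puts the emphasis on time to remission rather than on overall safety. The primary working hypothesis in Section 3 concerns time to remission only.

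**The concern.** Liver worsening is a harm that the protocol itself expects from hydroxychloroquine. 5.A and 5.H.3 list slight, transient rises in liver tests, and 4.L gives a liver-based stopping criterion for this drug alone. Items 6 to 8 keep participants with liver-related risk off the drug, and item 9 does so for advanced renal disease. The assignment rule then places them in the comparator. Phlebotomy's background rate of liver events therefore includes a high-risk group that has no counterpart on hydroxychloroquine. 4.O records serious events whatever their cause, so events unrelated to phlebotomy count as well.

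At stake is any statement that the two treatments are equally safe. 1.B intends the results to guide the choice of treatment in practice, and 1.B is where a reader will find the safety claim.

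**Working it through.** The documents give no rate, margin or power for safety, so there is no planned figure to reproduce.

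**Step 1: who can be where.**

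| Risk | Table 3 (bars hydroxychloroquine) | Table 4 (bars phlebotomy) | Group when treated |
|---|---|---|---|
| Continued heavy drinking | item 6 | none | phlebotomy |
| Hepatotoxic drugs | item 7 | none | phlebotomy |
| Marked liver-test abnormality | item 8 | none | phlebotomy |
| Creatinine above 3 mg/dL | item 9 | none | phlebotomy |
| Severe marrow dysfunction with anemia | none | item 2 | hydroxychloroquine |

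Liver-related risk moves one way. Risk of serious events in general moves both ways.

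**Step 2: does the planned analysis deal with it?** The balance check in 4.R covers susceptibility factors, and its multivariate analysis concerns response. Alcohol use appears there as present or absent. Baseline liver tests, hepatotoxic drugs and creatinine are not listed. 4.R says that assignment by medical reason will be considered, but for the susceptibility-factor analysis. Nothing of this kind is stated for safety.

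**Step 3: possible size.** All rates and shares here are assumed. Let s be the share of the phlebotomy group with an item from 6 to 9. Take a risk of 0.40 in those patients, 0.10 in all others, and no treatment effect.

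- Phlebotomy risk = 0.40s + 0.10(1 − s).
- Apparent risk ratio, hydroxychloroquine to phlebotomy = 0.10 / phlebotomy risk.
- If hydroxychloroquine's true risk is 0.15 (like-for-like ratio 0.15/0.10 = 1.5), the apparent ratio = 0.15 / phlebotomy risk.

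| s | Phlebotomy risk | Apparent ratio, true 1.0 | Apparent ratio, true 1.5 |
|---|---|---|---|
| 2% | 0.106 | 0.94 | 1.42 |
| 5% | 0.115 | 0.87 | 1.30 |
| 10% | 0.130 | 0.77 | 1.15 |
| 15% | 0.145 | 0.69 | 1.03 |
| 20% | 0.160 | 0.625 | 0.94 |

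With no true effect the ratio is 1/(1 + s(k − 1)), where k is the relative risk of the high-risk patients. It depends on s and k, not on the absolute rate. With k = 2 and s = 5% it is 1/1.05 = 0.95.

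**Step 4: a second set of assumed rates, as differences.** Take 5% in ordinary phlebotomy patients and 15% on hydroxychloroquine, a true excess of 10 points. With risk r in the high-risk patients, the masked share is s(r − 0.05)/0.10.

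- s = 2%, r = 20% to 60%: 3% to 11% masked.
- s = 5%, r = 40%: 0.05 × 0.35/0.10 = 17.5% masked; 8.25 points remain.
- s = 10%, r = 40%: 35% masked; 6.5 points remain.
- s = 20%, r = 40%: 70% masked; 3 points remain.
- s = 20%, r = 60%: 110% masked; the sign reverses (−1 point).

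The distortion is modest at small shares and serious only at high shares or strong risk contrasts.

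**The case against.** The strongest reply is that the protocol does not set out to compare safety: 4.B disclaims it and 5.H plays it down. The sentence on including all who start treatment follows the one on Cox models, so its reach to the safety tables is partly inferred. No pooled safety risk ratio is planned. The interim analysis reported no significant side effects with either treatment, and 4.E says that the alcohol item seldom applies, so the high-risk share may be small.

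Much of this stands. It limits the size and shows that the documents disagree on whether safety is compared. It does not remove the problem. 1.B still makes the claim, 4.R still says that safety measures will be compared, and the two-group structure offers no other set. The interim similarity was between randomized and nonrandomized participants, not between treatment groups on hepatic or renal risk.

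Four stronger readings are tempting and are not supported:

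- *All-cause serious events are biased in a known direction.* Table 4 sends marrow dysfunction with anemia to hydroxychloroquine, so the net direction is not established.
- *The plan will hide hydroxychloroquine's liver reaction.* Hepatic panels are scheduled during treatment, stopping reasons are recorded (4.H), and two of the stopping criteria in 4.L are relative to baseline. The reaction may still be seen within the group.
- *Every such patient goes to phlebotomy.* 4.Q provides for rare patients eligible for neither treatment.
- *Safety is a primary outcome.* The synopsis table is broken at that row, while 1.B and 4.K name normal plasma porphyrin as the primary outcome.

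The tilt also applies to events and threshold levels. Section 2 notes that liver abnormalities can improve with treatment, so in the pooled set a change from baseline could weaken or reverse it.

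**Conclusion.** The point holds for the between-group reading. By rule, hepatic, heavy-alcohol, hepatotoxic-drug and advanced-renal risk enters only the phlebotomy group among treated participants, and 4.R plans nothing to separate it. Pooled liver-event tables are tilted in favour of hydroxychloroquine and cannot support the safety half of the 1.B hypothesis. For serious events of any cause the groups are not comparable, with direction unknown.

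The size cannot be fixed from the documents. The range of 0.87 to about 0.62 rests on assumed risks of 40% and 10% and an assumed share of 5% to 20%. A smaller share or a weaker contrast gives less. The change is worth making because it affects analysis wording only.

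**What to change.** 1. Reconcile 1.B with 4.B and 5.H: state whether comparative safety is a conclusion of this study.
2. If any comparative safety statement is kept, base it in 4.R on participants with no medical contraindication in Table 3 or Table 4. These are all items other than unwillingness, taken from the reasons recorded under 4.E. Within that set, compare liver tests as change from baseline.
3. Keep the all-treated safety tables as supportive. Split them by medically contraindicated to one treatment versus medically eligible for both, and state that the pooled rates do not support the comparative safety conclusion. Show the randomized subset alongside.

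Cost: wording and one extra split, with no new data provided that liver tests are done alike in both groups. 4.F limits serum chemistries during phlebotomy treatment to clinical indication, whereas the Schedule of Events places a hepatic panel in the treatment period. Those passages must be reconciled.

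The restricted set is smaller, so intervals widen. It also drops the iron-overload and *HFE* participants (items 11 to 13), who are not part of the liver argument. Preference-assigned participants remain, so some confounding stays. The randomized subset avoids that but is weak. With an assumed 24 per group, power for 5% versus 15% is about 21%, against about 40% for an unbiased comparison of an assumed 55 phlebotomy and 45 hydroxychloroquine participants. Report estimates with intervals, not a test.

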- 5. Normal pattern of urine porphyrins by HPLC

How quickly each of these targets and outcomes will be achieved will vary greatly among patients. Therefore, levels need to be followed closely to anticipate when visits are needed to document treatment outcomes. If less frequent visits than recommended are contemplated, site investigators should review laboratory results within 3 days of receiving the reports and determine when the next visit and the next set of tests should be done in order to document all primary and secondary outcomes.

To be considered an evaluable outcome, time to achieving each of the study outcomes listed above (e.g. time to achieving a normal plasma porphyrin level) will be documented by an abnormal finding (e.g. a high plasma porphyrin level) followed by normalization of that finding

(e.g. achieving a normal plasma porphyrin level) within a specified time interval, which is referred to as the *documentation window* for achieving that outcome. That interval/documentation window will be 4 weeks for achieving a normal plasma porphyrin concentration, and 8 weeks for achieving the later biochemical outcomes. Therefore, a single missed visit that is not within one of these windows should not lead to a missed verification of a treatment outcome.

The following study practices are recommended to document the major study outcomes:

- 1. A phlebotomy patient should return every 2 weeks after the ferritin falls to 60 ng/mL, in order to either 1) document a ferritin of 25 ng/mL on the day of the last phlebotomy, or if serum ferritin was not measured on the day of the last phlebotomy, 2) to document a ferritin level of <20 ng/mL ~2 weeks after the last phlebotomy.
- 2. Once the plasma porphyrin level drops to less than ~4 mcg/dL, this test should be repeated biweekly to ensure that, even if a visit is missed, normalization is captured within the 4-week documentation window, which will properly document time to this primary treatment outcome.
- 3. After the plasma porphyrin concentration is normal (<0.9 mcg/dL), visits should be scheduled at 4 week intervals until the other outcomes are achieved. If visits are missed intermittently, this will still allow capturing a change from abnormal to normal within an 8-week documentation window.

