centers in the U.S. The laboratory uses published methods and reports results with a clinically useful interpretation (70-72). Other laboratories can be used if equivalent results can be obtained. Although results from different laboratories are likely to be comparable, this has not been verified. Normal ranges are likely to be less comparable between laboratories than elevated abnormal values. It is desirable to use the same laboratory for porphyrin testing throughout the study. In general, Quest, LabCorp, ARUP or Mayo are suitable for urine and plasma porphyrin measurements. However plasma porphyrin fluorescence peak testing is only done at UTMB and ARUP. The treatment outcomes are based on criteria stated in this protocol rather than on normal ranges stated by different laboratories, which may vary considerably.

Molecular analyses to identify *UROD* mutations are provided by the Genetic Testing Laboratory at the Icahn School of Medicine at Mount Sinai in New York City.

4.B. Design. This is an open-label comparative study of the two standard treatments for PCT. Participants will be assigned to the treatment for which they are eligible, as determined by strict medical criteria as outlined in this protocol. Participants eligible and willing to receive either treatment will be randomized across sites; however the majority of participants are expected to be assigned a treatment based on their medical indications and preference. Based on many decades of clinical experience, both treatments are accepted as effective and safe. Therefore, comparing efficacy and safety will not be an objective of these standard of care treatments. Rather, the main objectives will be to compare time needed to achieve remission, as assessed by documented primary and secondary biochemical and clinical outcomes, and the durability (i.e. lack of disease recurrence) after each treatment. Since phlebotomy and low dose hydroxychloroquine are both considered accepted alternatives for treatment of PCT, costs will be either considered standard of care and charged to insurance or supported by the Porphyrias Consortium grant for those participants without insurance.

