- **4.J. Study duration and end of study.** The duration of the study including the Follow Up Phase is at least five years. It is possible that the study will be extended further depending on results and the availability of funding. Subjects will enter the study needing treatment, and require up to 24 months of treatment and observation to document achieving the treatment outcomes, followed by at least 3 years of follow-up. Therefore, the most frequent study visits will occur during the Treatment Phase and generally the first ~12 months of the study, which includes active treatment and the treatment outcome windows to document biochemical remission. Based on the interim analysis (45) it is anticipated that the first outcome (a normal plasma porphyrin concentration) will be reached within 6-7 months, on average. Other treatment outcomes should be achieved within ~12 months, although this is uncertain at present, since such observations were not part of the interim analysis.
- **4.K. Treatment outcomes and schedule of events.** A schedule of events in tabular form and a study flow diagram are shown below. This study compares time to reaching certain efficacy outcomes with the two treatments and documents durability of treatment in terms of absence of increases in porphyrins and recurrence of symptoms.

The primary efficacy outcome is achieving a normal plasma porphyrin concentration (<0.9 mcg/mL). Secondary efficacy outcomes include achieving (1) absence of a fluorescence peak in diluted plasma at neutral pH; (2) a normal level of total urinary porphyrins; (3) a normal pattern of individual porphyrins in urine (defined as total highly carboxylated porphyrins less than coproporphyrin); (4) times to achieving intermediate improvements in these porphyrin

measures, which will be defined during data analysis; (5) absence of new skin lesions for at least 3 months; and (6) effects of susceptibility factors such as hepatitis C, inherited UROD deficiency, etc. on achieving these treatment outcomes.

Durability of treatment (i.e. absence of recurrence) is recorded as beginning with the time that treatment achieves the treatment outcomes, and extends to the time of repeat documentation of a normal plasma porphyrin concentration, assuming there have been no interim recurrences of skin manifestations.

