| Follow Up Lab tests- Hepatic Function Panel with reflex to PT and aPTT if abnormal, HCV RNA if positive at baseline | | х | х |
| Serum Ferritin [®] (follow up needed only for phlebotomy participants) | Х | х | Х |
| Dispense HCQ or begin phlebotomies | | X | |
| HCQ twice weekly or ~biweekly phlebotomies\$ | | Х | |
| Investigator review of labs to determine next visit | | PRN | X |
| Collection of urine for research testing | Х | X | X |

[figure not shown]
#Plasma porphyrin scan at neutral pH can be done at UTMB or ARUP, urine and plasma porphyrin measurements can be done at UTMB, ARUP, Mayo, Quest or LabCorp. During treatment phase once plasma levels drop to less than ~5 mcg/dL the test should be repeated biweekly

@ Serum ferritin should be done biweekly once the level drops below 60 ng/mL, until the target of ≤20 ng/mL is reached

[%]Complete Metabolic Panel should include- sodium, potassium, chloride, carbon dioxide, blood urea nitrogen, creatinine, total protein, albumin, total bilirubin, glutamic oxaloacetic transaminase [aspartate aminotransferase], serum glutamic pyruvic transaminase [alanine aminotransferase], glucose, uric acid, calcium, and phosphorous

^{\$} For participants on HCQ the coordinator will need to complete compliance forms monthly. For participants on phlebotomy the phlebotomy visit sheet will need to completed at every phlebotomy visit

Study flow diagram:

2. Laboratory evaluations

The tests listed below are required to assess safety of treatment or detect concurrent conditions that might affect treatment indications. Examples of the latter include advanced liver disease, chronic renal disease and myelofibrosis and other bone marrow disorders. The serum pregnancy test is needed in women of child-bearing potential to exclude pregnancy, because this is a reason for exclusion at the start of the study or for stopping treatment during the study.

- a. The following will be measured by the hospital clinical laboratory.
 - i) Tests done at baseline
 - Erythrocyte glucose-6-phosphate dehydrogenase activity

- Prothrombin time
- Partial thromboplastin time
- Total protein
- Albumin
- Total bilirubin
- Aspartate aminotransferase (glutamic oxaloacetic transaminase)
- Alanine aminotransferase (glutamic pyruvic transaminase)
- Iron
- Iron binding capacity
- Transferrin percent saturation
- Ferritin

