The study will continue as a more pragmatic study relevant to clinical practice, with assignment to treatment based on uniform criteria and randomization only of participants eligible for both treatments, to avoid unnecessary bias. Therefore, it will be a two-group study with no substudy. A descriptive approach to data analysis will be employed, with clinically relevant comparisons of the two treatments, rather than a noninferiority analysis.

Inclusion of all available participants rather than just the minority that can be randomized has a number of advantages. Participants eligible for both treatments (and therefore eligible for randomization) might respond differently than those who are not, since some of the reasons that make participants ineligible for one treatment relate to certain susceptibility factors and to prior treatment experience. Exclusion of a majority of participants from treatment comparisons also would make the study less pragmatic and less clinically relevant. In the interim analysis, randomized and nonrandomized participants did not differ in terms of clinical and demographic

features, but such important comparisons would be more meaningful with a larger number of participants. In the amended study, participants who are eligible for both treatments are to be randomized as a method for choosing between treatments that is needed in the study to avoid bias, but not as a study design feature. Bias might arise, for example, from existing site-specific treatment preferences.

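### One fixed plasma limit is applied to results from several laboratories whose agreement is unverified, so recorded remission times may partly reflect which laboratory was used

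*Combined protocol and SAP*

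**What the plan says.** Section 4 sets the limit in its recommended study practices: "After the plasma porphyrin concentration is normal (<0.9 mcg/dL), visits should be scheduled at 4 week intervals". The Background section gives the same limit.

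The Schedule of Events footnote says that "urine and plasma porphyrin measurements can be done at UTMB, ARUP, Mayo, Quest or LabCorp". Section 4.A goes further: "Other laboratories can be used if equivalent results can be obtained". It names no test of equivalence. It expects laboratories to be comparable but says this has not been checked, and it calls one laboratory throughout the study desirable rather than required. It then states: "Normal ranges are likely to be less comparable between laboratories than elevated abnormal values". Its remedy is a common criterion: "The treatment outcomes are based on criteria stated in this protocol rather than on normal ranges stated by different laboratories, which may vary considerably".

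Two further passages bear on the fix. Section 4.M lists the plasma fluorescence spectrum among the measurements made at each visit. Of that test, section 4.A says: "However plasma porphyrin fluorescence peak testing is only done at UTMB and ARUP".

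Section 4.R compares times to remission with Cox models and names susceptibility factors as covariates. It mentions no laboratory or site term, no cross-calibration and no sensitivity analysis by laboratory.

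**The concern.** A protocol-wide limit stops each laboratory from applying its own definition of normal. It does not make the assays read alike. If one laboratory reads higher than another at the same true concentration, its participants cross 0.9 mcg/dL later on paper.

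Three things depend on this.

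- **Absolute times to remission.** The Abstract and section 4.R present these as reference information for judging future treatments. A calibration difference moves them even when the treatment groups use laboratories in the same proportions.
- **The 4-week documentation window.** An event needs an abnormal and then a normal result within 4 weeks. A change of laboratory in that interval could create or hide the event with no biological change.
- **The treatment comparison.** Most participants are not randomized. If laboratory follows site, and treatment choice also varies by site, a laboratory difference could appear as a treatment difference.

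**Working it through.** The plan gives no between-laboratory bias, so there is no figure to reproduce. The bias below is assumed; the other inputs come from the documents unless marked.

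**Inputs**
- Limit: 0.9 mcg/dL (Background; section 4).
- Pretreatment level B: generally 10-25 mcg/dL (Background, treatment by phlebotomy).
- Time to the limit T: 6-7 months in both groups (Background, interim analysis).
- Documentation window: 4 weeks, or 28 days (Table 5).
- Between-laboratory bias b: not given; 10% to 50% either way is assumed.
- Decline: exponential (assumed); 30.4 days per month.

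**Unit check.** Section 4.K prints the limit as "The primary efficacy outcome is achieving a normal plasma porphyrin concentration (<0.9 mcg/mL", which equals 90 mcg/dL and lies above the usual untreated level. The entry criterion of more than 2.7 ug/dL, or 3-fold the upper limit, gives 3 x 0.9 = 2.7. So mcg/dL is the consistent unit, and section 4.K should be reconciled with it.

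**Shift in one participant's date.** With C(t) = B·exp(-kt), k = ln(B/0.9)/T. A laboratory reading (1+b) times the reference moves the crossing by ln(1+b)/k.

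- Fastest decline (B = 25, T = 6): k = ln(27.8)/6 = 0.554 per month.
- Slowest decline (B = 10, T = 7): k = ln(11.1)/7 = 0.344 per month.
- 20% high: ln(1.2) = 0.182. The delay is 0.182/0.554 x 30.4 = 10 days to 0.182/0.344 x 30.4 = 16 days.

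| Assumed bias | Reads high: delay (days) | Reads low: advance (days) |
|---|---|---|
| 10% | 5-8 | 6-9 |
| 20% | 10-16 | 12-20 |
| 30% | 14-23 | 20-32 |
| 50% | 22-36 | 38-61 |

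At T = 6.5 months, a reading 19-27% high costs 14 days, and one 41-60% high costs the full 28-day window.

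**Effect on the treatment comparison.** A Cox comparison was simulated with 50 per group and equal true times (lognormal, median 6.5 months, log-SD 0.4, assumed), two-weekly testing and 400 runs per case. Entries are hazard ratios; the true value is 1.

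| Share of each group using the high-reading laboratory | 20% bias | 30% bias | 50% bias |
|---|---|---|---|
| 20% and 20% | 1.01 | 0.99 | 0.99 |
| 10% and 30% | 0.96 | 0.95 | 0.94 |
| 0% and 40% | 0.96 | 0.91 | 0.87 |

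With no bias the same simulation gave 0.99-1.02, which shows its noise. The highest rejection rate under imbalance was about 9% (0% and 40%, 50% bias), against a nominal 5%.

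A second simulation used Weibull times (shape 2, assumed), 20% bias and 20 participants outside UTMB. Splits of 8/12 and 5/15 gave about 0.99 and 0.98. Putting all 20 in one group, the extreme case, gave about 0.93-0.96, with rejection near 6%.

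**How many participants are exposed.** Section 4.D expects 40-50 of about 60 new participants at UTMB, leaving 60 - 50 = 10 to 60 - 40 = 20 elsewhere. The Background says 52 had already been enrolled there and that later enrolment was mostly there too. So 20 participants outside UTMB is a reasonable working figure, if UTMB participants use the UTMB laboratory. Section 4.A permits that but does not require it.

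**The case against.** The strongest reply is that section 4.A has already dealt with the problem. Read plainly, its sentence on normal ranges is about reference ranges, and the common criterion answers it. The section also expects comparable results, admits other laboratories only on a condition of equivalence, and favors one laboratory throughout. Most participants are at UTMB. Since the fluorescence scan already takes plasma to UTMB or ARUP, many primary totals may be measured there anyway.

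Much of this stands. It limits the size of the problem, and the plan nowhere says that assay agreement is worst near 0.9 mcg/dL. It does not close the gap. The equivalence condition has no test, the same-laboratory preference is not a rule, and nothing requires the plasma total to come from the laboratory that does the scan.

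Three stronger readings are tempting but unsupported.

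- A reader might take the shift as a direct bias of the treatment comparison. At 20% bias and Weibull shape 2, (1 + shift)^-2 gives a hazard ratio near 0.87-0.90. That requires every participant in one group, and none in the other, to use the high-reading laboratory. The enrolment figures point away from this.
- A reader might infer that some laboratory cannot report below 0.9 mcg/dL and so never records the event. The documents give no reporting limit for any laboratory, and such a laboratory would fail the equivalence condition.
- Section 4.R says "Bias might arise, for example, from existing site-specific treatment preferences". A reader might take this as an admission of uncontrolled site bias. It is the plan's reason for randomizing participants eligible for both treatments. It leaves the non-randomized majority unprotected, but it does not show that laboratory follows site.

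**Conclusion.** The point holds as a correctable weakness in measurement and analysis. The primary event date can depend on the laboratory, agreement between laboratories is unverified, and the analysis has no means of detecting or adjusting for a difference.

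The size is unknown. A 20% high reading would delay a recorded date by about 10-16 days, under 8% of the time to remission (16/213 days = 7.6% in the slowest case). That bears directly on the reference times, whatever the balance between groups. The treatment hazard ratio stays near 1.0 if laboratory use is balanced. It is about 0.96-0.99 under partial imbalance at 20% bias, and moves further only with larger bias or a more extreme split.

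These figures rest on exponential decline, the assumed bias and the assumed spread of remission times. They do not show that the trial's comparison is biased.

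**What to change.** **Future samples.** Amend section 4.A and the Schedule of Events footnote so that the plasma total documenting the primary outcome is read from the sample already sent to UTMB or ARUP for the fluorescence scan. Require the same one of the two to be kept for each participant. Plasma totals from other laboratories would serve only to time visits.

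**All results, including those already collected.** Record the measuring laboratory with each value. This matters because the protocol version is dated February 2020, activation was in 2011, and data from 2006 onward are to be included; new wording cannot re-assay those samples.

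**Analysis.** In section 4.R, stratify the primary Cox model by laboratory, or specify that as a sensitivity analysis. It is needed even after the change above, because agreement between UTMB and ARUP is also unverified.

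**Cost.** The work is wording changes and one recorded field. Sites lose their choice of local laboratory for the plasma totals that count, and stratification costs a little precision. Shipping should change little, because the scan already requires it.
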